### 6.7 Physical Examination

A physical examination will be performed by the Investigator at screening. The following areas will be included:

- General inspection
- Neck veins / pulses
- Oral cavity / teeth (for assessment of abnormalities possibly affecting sublingual absorption)
- Palpation of precordium and auscultation of the heart
- Auscultation of chest
- Abdominal examination (liver, spleen, and lower abdomen)
- Peripheral pulses (radial and foot)
- Assessment of reflexes (biceps, knee, and ankle)

Any abnormalities will be recorded.

## **6.8 Vital Signs Measurements**

Vital signs (body temperature, respiratory rate, heart rate, and blood pressure) will be measured at screening and on study Day 1. Vital signs will be measured after resting in the supine position for at least 5 minutes.

## **6.9 Drug Screen**

A urine sample will be taken at screening, study Day 1, and at weekly visits during the study to test for the following drugs of abuse: amphetamines, barbiturates, benzodiazepines, cocaine metabolite, marijuana metabolite, methadone, opiates, phencyclidine, propoxyphene, and buprenorphine.

Precautions should be taken to prevent manipulation of the urine sample by the subject.

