## 1. INTRODUCTION

### 1.1 Background

In 2017, 70,237 drug overdose deaths occurred in the United States. The age-adjusted rate of overdose deaths increased significantly by 9.6% from 2016 (19.8 per 100,000) to 2017 (21.7 per 100,000). Opioids, primarily synthetic opioids other than methadone, are currently the main driver of drug overdose deaths and were implicated in 47,600 overdose deaths in 2017 (67.8% of all drug overdose deaths). [2]

Effective and available treatment is the gateway to reducing the morbidity and mortality associated with drug addiction. Medication-assisted treatment (MAT), the current standard for opioid addiction, is the use of medications, in combination with counseling and behavioral therapies, to provide a “whole-patient” approach to the treatment of opioid use disorder (OUD). Research shows that MAT can successfully treat opioid use disorder (OUD), and for some people can help sustain recovery. [3]

Successful MAT implementation requires the availability of varying levels and types of care in a range of settings, although all of the necessary services may not be available to all patients. Patients appropriate for outpatient care require access to office-based buprenorphine prescribing (or opioid treatment programs that provide methadone) and clinical behavioral health services. However, the National Center for Health Workforce Analysis estimates that between 40 million and 45 million individuals (roughly 20 percent of the U.S. 2013 population) may have needed but did not receive behavioral health care in 2013. The National Center completed a projection of US supply and demand for behavioral health practitioners in 2025 and identified six provider types that are tracking for shortage of more than 10,000 full-time equivalents: psychiatrists; clinical, counseling, and school psychologists; substance abuse and behavioral disorder counselors; mental health and substance abuse social workers; mental health counselors; school counselors. [4]

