## **4. SELECTION OF STUDY POPULATION**

### **4.1 Inclusion Criteria**

A subject must meet the following criteria to qualify for the study.

1. Male or female 18 – 65 years of age at the screening visit, fluent in English and able to read, comprehend, and willingly sign the informed consent form (ICF).

2. Voluntarily seeking treatment for OUD.
3. In the judgment of the Investigator has the appropriate hearing, vision, manual dexterity, ability to understand instructions, and ability to use and understand internet-based applications.
4. Currently meets the criteria for moderate or severe opioid use disorder according to Diagnostic and Statistical Manual of Mental Disorders (DSM)-V (Appendix B).
5. Has a positive UDS for opioids at screening that is consistent with their drug use history.
6. In good health as determined by lack of clinically significant abnormalities in health assessments performed at screening.
7. Agrees not to take any buprenorphine products other than those prescribed by the Investigator during participation in the study, and agrees to use OXD01 as directed if randomized to that treatment group.
8. Completed SL BUP/NAL induction, with physical withdrawal symptoms reduced so the subject is able to fully participate in OXD01 training, if randomized to that treatment group, and is no greater than 14 days from the first dose of SL BUP/NAL induction.

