## **6.11 Timeline Followback Method – Drug and Alcohol Use**

The TLFB is a self-assessment used to document recent use of opioids, other illicit drugs of abuse, and alcohol. A TLFB assessment will be completed on study Day 1, and at weekly visits while on study treatment. Subjects will be asked to estimate both drug and alcohol use during the 7 days prior to the study visit on Day 1 and Week 25. Subjects will be asked to estimate only drug use during the 7 days prior to the study visit on Weeks 2-24. The TLFB is a closed Yes or No question of drug or alcohol use (Appendix D, E).

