### **11.3 Primary Objective**

The primary objective of the study is to determine whether the combination of SL BUP/NAL SOC background therapy and the digital therapeutic OXD01 is superior to SL BUP/NAL alone to reduce opioid use, as measured by the treatment success rate. Treatment success is defined as the subject having  $\geq 80\%$  of urine drug tests negative for opioids plus  $\geq 80\%$  of self-reports negative for illicit opioid use (from the TLFB interview at the same visit) from Week 6 to Week 25. Each subject will be evaluated as a success or failure for this metric and the proportion of subjects in each group demonstrating  $\geq 80\%$  of urine drug tests negative for opioids plus negative self-reports for illicit opioid use (from the TLFB interview) will be tested using chi-squared test.

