**✓ WHAT TO FILL IN**

- The idea is that for **each day** on the calendar we want you to indicate whether you "used" or "did not use" drugs or alcohol. Specifically indicate whether you have used any of the following: amphetamines (uppers), barbiturates, benzodiazepines (for example, Xanax, Ativan, Valium), cocaine, marijuana, methadone, opiates (for example, oxycodone, hydrocodone), phencyclidine (PCP), or alcohol in any form.
- On days when you **did not use drugs or alcohol**, you should write a "0" in the box.
- On days when you **did use drugs or alcohol**, you should put a "✓" in the box for drugs or alcohol.

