**✓ WHAT TO FILL IN**

- The idea is that for **each day** on the calendar we want you to indicate whether you "used" or "did not use" drugs. Specifically indicate whether you have used any of the following: amphetamines (uppers), barbiturates, benzodiazepines (for example, Xanax, Ativan, Valium), cocaine, marijuana, methadone, opiates (for example, oxycodone, hydrocodone), phencyclidine (PCP).
- On days when you **did not use drugs**, you should write a "0" in the box.
- On days when you **did use drugs**, you should put a "✓" in the box.

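### Neither the protocol 6.9 urine panel nor the TLFB forms name the synthetic opioids that section 1.1 puts at the centre of the overdose problem, so unreported use of them may be scored opioid-negative on the primary endpoint

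*Protocol*

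**What the plan says.** **Urine test.** Protocol 6.9 applies one list at screening, Day 1 and every weekly visit: "amphetamines, barbiturates, benzodiazepines, cocaine metabolite, marijuana metabolite, methadone, opiates, phencyclidine, propoxyphene, and buprenorphine". Four of the ten entries are opioid-related: methadone, opiates, propoxyphene and buprenorphine.

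**Self-report.** The Appendix D form (Day 1 and Week 25) ends its drug list with "methadone, opiates (for example, oxycodone, hydrocodone), phencyclidine (PCP), or alcohol in any form". The Appendix E form (Weeks 2-24) has the same opioid entries. Protocol 6.11 describes a wider purpose: "The TLFB is a self-assessment used to document recent use of opioids, other illicit drugs of abuse, and alcohol".

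**Background.** Protocol 1.1 says: "Opioids, primarily synthetic opioids other than methadone, are currently the main driver of drug overdose deaths".

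**Endpoint.** Under protocol 11.3 and SAP 3.4.1, success needs at least 80% of urine tests negative for opioids plus at least 80% "of self-reports negative for illicit opioid use (from the TLFB interview at the same visit) from Week 6 to Week 25". SAP 3.4.1 imputes missed and post-withdrawal visits as positive on both components.

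**Entry.** Inclusion criterion 5 reads: "Has a positive UDS for opioids at screening that is consistent with their drug use history".

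**SAP on the urine test.** SAP 3.5.2 repeats the ten analytes, but for a dipstick at screening and Weeks 1-5. It promises descriptive UDS statistics for Weeks 6-25 without naming a panel. Neither document says which analytes make a test negative for opioids.

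**The concern.** The primary objective is reduced opioid use, and the endpoint rests on two instruments only. The panel gives methadone, propoxyphene and buprenorphine their own lines, which suggests that its opiates line is not meant as a catch-all. No line is left for other synthetic opioids, and the form completed by the subject does not prompt for them.

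Two things are at stake. If such use goes unseen at similar rates in both arms, true failures become successes, the difference between arms shrinks and power falls. If it goes unseen at different rates, the comparison is biased. The trial is open-label, and a urine test that misses the drug provides no check on the self-report.

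**Working it through.** **1. The plan's own figure.** Inputs: 12% vs 25%, about 200 per arm, 90% power, Fisher's exact test (protocol 11.6, SAP 2.2.4); two-sided 0.05 (SAP 3.1.5); 1:1 allocation.

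- Uncorrected chi-squared: n = [1.960·√(2·0.185·0.815) + 1.282·√(0.12·0.88 + 0.25·0.75)]² / 0.13² ≈ 186 per arm.
- With continuity correction, which approximates Fisher: 201 per arm.
- Exact enumeration at 200 per arm: Fisher power 90.4%, uncorrected chi-squared power 92.6%.

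The stated size reproduces on the Fisher basis. The planned primary test is chi-squared, so 92.6% is the reference below.

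**2. Equal misclassification (illustration).** Let f be the share of all true failures scored as successes, the same in both arms. The documents give no value for f. The observed rate is p′ = p + (1 − p)·f. For f = 5%: control 0.12 + 0.88 × 0.05 = 16.4%; OXD01 0.25 + 0.75 × 0.05 = 28.75%. Power is exact chi-squared at 200 per arm.

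| f | Control | OXD01 | Difference | Power |
|---|---|---|---|---|
| 0 | 12.0% | 25.0% | 13.0 points | 92.6% |
| 2% | 13.8% | 26.5% | 12.7 points | 89.6% |
| 5% | 16.4% | 28.8% | 12.4 points | 84.6% |
| 10% | 20.8% | 32.5% | 11.7 points | 75.8% |

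This treats 12% and 25% as rates under complete detection. The 12% is a literature rate, and the documents do not say which assay lay behind it.

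**3. Which failures can flip.** Weeks 6-25 hold 20 visits, so success needs at least 16 negative urine tests and at least 16 negative self-reports (0.80 × 20 = 16). A subject who misses more than four visits fails on imputation, whatever the assay detects. If, as an assumption, half of all failures are of that kind, then 5%, 10% or 20% flipping among the rest means an overall f of 2.5%, 5% or 10%, with power 88.8%, 84.6% or 75.8%.

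**4. Unequal misclassification (illustration).** Take no true effect, 12% in both arms, with 5% of control failures and 10% of OXD01 failures flipping. The observed rates are 16.4% and 0.12 + 0.88 × 0.10 = 20.8%. The chance of a significant result favouring OXD01 is about 20% (normal approximation), against a nominal 2.5% in that direction.

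**5. Which panel applies in Weeks 6-25.** Protocol 6.9 says the ten-analyte list, at every weekly visit. SAP 3.5.2 gives that list only up to Week 5. No other panel is described, so protocol 6.9 is the sole specification of the endpoint test.

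**The case against.** The case on the other side has five parts.

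- **Detection is not documented either way.** No assay, cut-off or cross-reactivity is given, and the documents use the terms loosely: criterion 5 asks for a screen positive for opioids, and the TLFB forms put oxycodone and hydrocodone under opiates. This stands. A miss is possible, not shown.
- **The self-report is not closed to these drugs.** The entry gives examples only, section 6.11 says opioids, and nothing tells a user of a synthetic opioid to record no use. A subject who reports use at more than 20% of visits fails even if urine misses it. This stands: the gap is a missing prompt, and a false negative on both components also requires non-reporting.
- **Criterion 5 screens at entry.** If the panel misses these drugs, people who use nothing else would largely be kept out. This stands, but it does not cover mixed use or a switch after entry.
- **Another test may have been used in Weeks 6-25.** The SAP wording leaves room for that, but neither document specifies one.
- **The value of f has no source.** This also stands. Section 1.1 describes 2017 overdose deaths in the United States, not use among treatment-seeking trial subjects.

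**Conclusion.** The point holds as a gap in how the primary endpoint is ascertained. As written, the plan neither tests for nor prompts for a class of opioid that its own background section puts first, and the SAP does not say which panel serves the endpoint window. Unreported use of that class can therefore be scored opioid-negative on both components, provided the opiates assay does not detect it.

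The size is unknown. With equal flipping of 2% to 10% of all failures, power runs from about 90% to 76%. At 2% it is essentially the stated 90%. Imputed failures cannot flip and criterion 5 narrows the group at risk, and both pull f down. Unequal flipping would bias the result as well as dilute it, but nothing in the documents shows that it would differ by arm.

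A reader might infer that the endpoint is blind to these drugs and the trial underpowered as a result. The documents do not support that: non-detection is an assumption, the self-report can still capture the use, and no rate is given.

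**What to change.** (a) In TLFB Appendices D and E, name fentanyl/synthetic opioids, and heroin, among the opioid examples. This is a wording change at no cost. Neither document names an individual drug of this synthetic class, so fentanyl is offered here as the example.

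(b) Add a fentanyl/synthetic-opioid analyte to the protocol 6.9 panel, and state in the SAP that this panel applies to the Week 6-25 endpoint tests. It runs on urine already collected, with no new visit or sample. The cost is the assay: about 400 × 20 = 8,000 samples in Weeks 6-25, or 510 + 400 × 25 = 10,510 if every visit including screening is covered.

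(c) In the same edit, state which analytes make a test opioid-positive for the endpoint, with prescribed buprenorphine not counted. This is wording only.

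SAP 3.2.2 already counts enrolled subjects at two sites, so some samples may have been tested and some forms completed. Where (a) and (b) can no longer be applied, the SAP should still name the Week 6-25 panel actually used, make edit (c), and report whether that panel detects synthetic opioids.

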## **6.10 Quantity-Frequency Index**

The Quantity-Frequency Index (QFI) is a self-assessment of the frequency and quantity of alcohol consumption over the previous 30 days. The QFI is comprised of the following two questions:

During the past 30 days:

1. How often do you have a drink containing alcohol?

- (0) Never
- (1) Monthly or less
- (2) 2 to 4 times a month
- (3) 2 to 3 times a week
- (4) 4 or more times a week

2. How many drinks containing alcohol do you have on a typical day when you are drinking?

- (0) 1 or 2
- (1) 3 or 4
- (2) 5 or 6
- (3) 7, 8, or 9
- (4) 10 or more

The QFI will be completed on study Day 1 and at the visit on Week 25.

## **6.11 Timeline Followback Method – Drug and Alcohol Use**

The TLFB is a self-assessment used to document recent use of opioids, other illicit drugs of abuse, and alcohol. A TLFB assessment will be completed on study Day 1, and at weekly visits while on study treatment. Subjects will be asked to estimate both drug and alcohol use during the 7 days prior to the study visit on Day 1 and Week 25. Subjects will be asked to estimate only drug use during the 7 days prior to the study visit on Weeks 2-24. The TLFB is a closed Yes or No question of drug or alcohol use (Appendix D, E).

#### 6.12 Review Study Restrictions

Study restrictions (Section 4.3) will be reviewed with the subject at study screening, and at the visits on Weeks 1-5, 7, 9, 11, 13, 17, and 21.

#### 6.13 Randomization and Allocation to Treatment, Subject Identification Number

Eligible subjects will be randomized on Day 1 through an IRT system (separate instructions will be provided).

Each subject will be identified by a unique randomization number assigned by the IRS system on Day 1. Prior to randomization, subjects will be identified by a screening number, assigned when the subject signs the ICF.

#### 6.14 Opioid Craving Visual Analog Scale

Cravings for opioids will be assessed by the subject through the use of a VAS, where 0 mm represents “no cravings” and 100 mm represents “the most intensive craving I have ever had.” The baseline craving VAS assessment will be collected on study Day 1 and at the visit on Weeks 5, 9, 13, 17, 21 and 25 (Appendix F).

#### 6.15 Quick Inventory of Depression Symptoms, Self-Report

Symptoms of depression will be assessed by the subject using the QIDS-SR (Appendix C) at screening and at the visit on Week 25. An overall score  $\geq 16$  (severe depression) or a rating of 2 or 3 for question 12 (Thoughts of Death or Suicide) at screening will exclude the subject from the study.

#### 6.16 Review Behavioral Health Therapies

Participation in behavioral health therapies since the previous visit, including 12-step programs, will be recorded at the visits on Weeks 1-5, 7, 9, 11, 13, 17, and 21.

#### 6.17 Clinical Global Impression

Clinical Global Impression (Severity) - Severity of opioid dependence will be assessed by the Investigator on study Day 1 and at the visit on Week 13 and Week 25 using the following assessment scale:

Considering your total clinical experience with this particular population, how mentally ill is the subject at this time?

- 0 = Not assessed
- 1 = Normal, not at all ill
- 2 = Borderline ill
- 3 = Mildly ill
- 4 = Moderately ill
- 5 = Markedly ill
- 6 = Severely ill
- 7 = Among the most extremely ill subjects

Clinical Global Impression (Improvement) – Improvement in severity of opioid dependence from baseline (study Day 1) will be assessed by the Investigator at the visit on Week 13 and Week 25 using the following assessment scale:

Rate total improvement whether or not, in your judgement, it is due entirely to drug treatment. Compared to his or her condition at admission to the project, how much has the subject changed?

- 0 = Not assessed
- 1 = Very much improved
- 2 = Much improved
- 3 = Minimally improved
- 4 = No change
- 5 = Minimally worse
- 6 = Much worse
- 7 = Very much worse

#### **6.18 End of Study Interview**

The following information will be obtained from the subject at the visit on Week 25, addressing the time from Day 1 through Day 169 (or early termination):

- Number of emergency department visits
- Number of hospitalizations
- Number of overdoses
- Able to resume work, school, or other productive activity (Yes, No, or No Change)

### **7. ADVERSE EVENTS**

#### **7.1 Definitions**

##### **7.1.1 *Adverse Event***

An adverse event is any untoward medical occurrence in a subject or clinical trial subject caused by, or associated with a device and which does not necessarily have to have a causal relationship with the device. An AE can therefore be any unfavorable and unintended sign, symptom, or disease temporally associated with the use of the device, whether or not considered related to the intended use of the device.

Pre-existing conditions will not be regarded as AEs if the condition follows a normal course of recovery, unless it worsens after exposure to the device. Medical procedures will not be regarded as AEs, but the cause of the procedure may be.

### 7.1.2 *Adverse Reaction*

An adverse reaction is all noxious and unintended responses in a subject using a medical device. The phrase related to a medical device means that a causal relationship between a device and an adverse event is at least a reasonable possibility; i.e., the relationship cannot be ruled out.

### 7.1.3 *Unanticipated Adverse Device Effect*

An unanticipated adverse device effect (UADE) is any serious adverse effect on health or safety, any life-threatening problem or death caused by, or associated with a device, if that effect, problem, or death was not previously identified in nature, severity, or degree of incidence in the device; or any other unanticipated serious problem associated with a device that relates to the safety or welfare of subjects.

### 7.1.4 *Serious Adverse Event*

An SAE is an AE that:

- results in death
- is life threatening
- requires hospitalization or prolongation of existing hospitalization
- results in persistent or significant disability/incapacity
- is a congenital anomaly/birth defect
- is another important medical event (e.g., convulsions not leading to hospitalization)

Medical and scientific judgment should be exercised in deciding whether expedited reporting is appropriate in other situations, such as important medical events that may not be immediately life-threatening or result in death or hospitalization but may jeopardize the subject's health or may require intervention to prevent one of the other outcomes listed in the definitions above. These AEs should also usually be considered as serious.

SAEs will only be considered when there is an underlying AE. For example, a hospitalization due to a pre-existing condition which is not due to an aggravation of the condition after exposure to any study treatment will not be considered to be an SAE.

## 7.2 Adverse Event Reporting Period

The AE reporting period will start after signing the informed consent form and will end at discharge from the study.

## 7.3 Collection of Adverse Event Data

The subjects will be monitored throughout the study for any AEs, including abnormal, clinically significant, laboratory values, clinically significant findings at physical examinations, vital signs measurements or electrocardiogram (ECG) measurements, spontaneous reports by study subjects and observations by the study personnel. AEs will be collected through both solicited and unsolicited means and subsequently coded in tabular form using the Medical Dictionary for Regulatory Activities Terminology (MedDRA) Version 14.1 or later AE dictionary. The subjects will be encouraged to report signs, symptoms, and any changes in health to the clinic staff. Severity of each AE will be determined by an Investigator based on observation and questioning of the subject.

## 7.4 Recording of Adverse Events

All AEs should be recorded in the CRFs. Although an AE can initially be acknowledged by anyone in the study team, an Investigator will always be responsible for reporting and assessments of AEs. All AEs should be reported separately (i.e. one record per event). Reporting of AEs are event based, (i.e., an ongoing event will not be closed until resolved or at the end of study). At least the following will be recorded for each AE:

**Description of adverse event:** Adverse event description should be provided in English. Diagnosis is to be preferred over symptoms. If no diagnosis could be made, each symptom will be reported as a separate AE. Abbreviations should be avoided. Descriptive words should be used for ongoing conditions as applicable (e.g. "exacerbation of herpes genitalis", "worsening of eczema" etc.).

**Serious adverse event:** Yes or no (definition of SAE in section 7.1.4). If Yes, an SAE Report Form needs to be completed.

**Maximum intensity:** Maximum intensity of the AE during the complete course of the event should be recorded in accordance with the following definitions:

- Mild – Awareness of sign and symptoms but easily tolerated
- Moderate – Discomfort sufficient to cause interference with normal activities
- Severe – Incapacitating, with inability to perform normal activities

**Duration:** The duration of the AE will be recorded by start and stop date and time.

**Relatedness to medical device (causality):** Relatedness to the medical device will be assessed by an Investigator according to the below categories.

- *Not related:* A causal relationship between the medical device and the AE is assessed as not possible (e.g. due to onset in relation to use of the device or that another cause of the AE has been identified)
- *Related:* A causal relationship between the medical device and the AE is assessed as at least possible

**Actions taken:** Actions taken in relation to the AE with respect to use of the medical device, should be recorded as:

- Use of the medical device withdrawn
- Use of the medical device interrupted
- Use of the medical device is reduced
- Use of the medical device is increased
- Use of the medical device not changed
- Not applicable
- Unknown

Any medication given to treat the AE will be recorded separately on the concomitant medication list of the CRFs.

**Outcome:** The outcome of the AE should be recorded.

- Recovered/Resolved
- Recovering/Resolving
- Not recovered/Not resolved
- Recovered/Resolved with sequelae
- Fatal
- Unknown – lost to follow-up

